1. LIST OF ABBREVIATIONS

| ABBREVIATION | DEFINITION |
|---------------------|--|
| AE | Adverse event |
| ANCOVA | Analysis of covariance |
| ANOVA | Analysis of variance |
| ATC | Anatomical Therapeutic Chemical |
| AUC | Area under the plasma concentration-time curve |
| AUC _{0-2h} | Area under the plasma concentration-time curve from time zero to 2 hours |
| BLQ | Below the limit of quantitation |
| BMI | Body mass index |
| C1, C2, C3, C4 | Cohort 1, Cohort 2, Cohort 3, Cohort 4 |
| C _{max} | Maximum observed plasma concentration |
| CNS | Clinical Network Services |
| COMT | catechol-O-methyl transferase |
| CRF | Case Report Form |
| CS | Clinically significant |
| CSR | Clinical Study Report |
| CTCAE | Common Terminology Criteria for Adverse Events |
| CV | Coefficient of Variation |
| DA | Dopamine Agonists |
| DBL | Database Lock |
| DBP | Diastolic blood pressure |
| DCI | Decarboxylase inhibitor |
| ECG | Electrocardiogram |
| FSH | Follicle Stimulating Hormone |
| H&Y | Hoehn & Yahr |
| HBsAg | Hepatitis B surface antigen |
| HCV-ab | Hepatitis C Virus Antibody |
| HIV | Human Immunodeficiency Virus |
| ICH | International Conference on Harmonization |
| ITT | Intension-to-Treat |
| L-dopa | Levodopa |
| LOCF | Last Observation Carried Forward |

CONFIDENTIAL AND PROPRIETARY

| ABBREVIATION | DEFINITION |
|---------------------|--|
| LOQ | Limit of quantitation |
| MAOB-I | monoamine oxidase-B inhibitor |
| MDS-UPDRS | Movement Disorder Society Unified Parkinson's Disease Rating Scale |
| MedDRA | Medical Dictionary for Regulatory Activities Terminology |
| MMRM | Mixed Model for Repeated Measures |
| N | Sample Size |
| NCA | Non-compartmental analysis |
| NCS | Not clinically significant |
| OC | Observed Cases |
| PD | Parkinson's Disease |
| PDyn | Pharmacodynamic |
| PK | Pharmacokinetic |
| POD | Precision Olfactory Delivery |
| PT | Preferred Term |
| QD | Administered once per day |
| SAD | Single ascending dose |
| SAE | Serious adverse event |
| SAP | Statistical analysis plan |
| SAS | Statistical Analysis System |
| SBP | Systolic blood pressure |
| SD | Standard Deviation |
| SMC | Safety Monitoring Committee |
| SOC | System Organ Class |
| SOP | Standard Operating Procedures |
| T _{max} | Time of observed maximum plasma concentration |
| t _½ | Elimination half-life |
| TEAE | Treatment Emergent Adverse Event |
| ULN | Upper limit of normal |
| WHODD | World Health Organization Drug Dictionary |

2. INTRODUCTION

This statistical analysis plan (SAP) for study (protocol: INP103-201) is developed based on Amendment 4 of the final protocol dated 01 February 2019 and CRF PDF Casebook generated on 20 March 2019. The purpose of this SAP is to ensure that all statistical results including the data listings, summary tables and figures which will be produced, and the statistical methodologies that will be used, are comprehensive and appropriate for the analysis of the study objectives specified in the protocol. Any amendments to the SAP will be made prior to final database lock and any additional analyses not described in the final SAP or deviation from the final SAP will be documented in the clinical study report (CSR).

This is a Phase IIa randomized, double-blind, placebo-controlled study, to compare the safety, tolerability and PK/PD_{yn} of L-dopa following administration of INP103 in the presence of a DCI to that of placebo to PD patients during an OFF episode.

3. STUDY OBJECTIVE(S) AND ENDPOINT(S)

3.1. Study Objective(s)

3.1.1. Primary Objectives

The primary objective of the study is:

- To compare the safety and tolerability of nasal single doses of INP103 in the presence of decarboxylase inhibitor (DCI) to that of placebo in patients with Parkinson's Disease (PD) during an OFF episode.

3.1.2. Secondary Objectives

The secondary objectives of the study are:

1. To characterize the pharmacokinetics (PK) of single doses of INP103
2. To explore the effect of single doses of INP103 versus placebo on motor function
3. To explore the PK/pharmacodynamic (PDyn) relationship of single doses of INP103 and motor function

3.1.3. Exploratory Objectives

The exploratory objective of the study is:

- To evaluate the plasma concentration-time profiles of carbidopa following single doses of INP103 in Cohort 4 and to determine PK parameters.

3.2. Study Endpoints

3.2.1. Primary Endpoints

Safety and tolerability, including the assessment of physical examinations (including nasal inspection), electrocardiograms (ECGs), vital signs (including supine and standing blood pressure, all other vital signs supine only), clinical laboratory results, and adverse events (AEs; specifically, overall dyskinesia assessments) over the immediate 240 minutes following dosing and over 7 days of follow-up.

These primary endpoints, specific to the full study analysis, will also be considered the primary endpoints for the interim analysis (reviewed in a blinded manner). The data for the primary endpoints will also be reviewed at each safety monitoring committee meeting in a blinded manner.

3.2.2. Secondary Endpoints

1. PK profile of L-dopa for 120 minutes following dosing with INP103 (AUC_{0-2h}, C_{max} and T_{max}).
2. Motor function, evaluated as:
 - Change from baseline to 30 minutes post-dose in Movement Disorder Society Unified Parkinson's Disease Rating Scale (MDS-UPDRS) Part III score (primary motor function endpoint).

- Change from baseline to 15, 30, 45, 60, 90 and 120 minutes post-dose for Cohort 1 (C1), Cohort 2 (C2), Cohort 3 (C3) and change from baseline to 30, 60, 90, 120 minutes for Cohort 4 (C4), in MDS-UPDRS Part III score.
 - Cumulative proportion of responders by post-dose time point (15, 30, 45, 60, 90 and 120 minutes for C1, C2, C3 and change from baseline to 30, 60, 90, 120 minutes for C4), where response is defined as an improvement of 30% in MDS-UPDRS Part III score from baseline.
 - Time to response, where response is defined as an improvement of 30% in MDS-UPDRS Part III score from baseline.
 - Duration of response, where response is defined as an improvement of 30% in MDS-UPDRS Part III score from baseline
 - Area Under the Curve (AUC) of changes in MDS-UPDRS Part III scores from pre-dose to 15, 30, 45, 60, 90 and 120 minutes for C1, C2, C3 and change from baseline to 30, 60, 90, 120 minutes for C4
 - Maximum response in MDS-UPDRS Part III scores from pre-dose to 15, 30, 45, 60, 90 and 120 minutes for C1, C2, C3 and change from baseline to 30, 60, 90, 120 minutes for C4
 - Subjective time to ON, as evaluated by the Investigator and by subject self-assessment
3. The PK/PD_{yn} relationship of single doses of INP103 and motor function

3.2.3. Exploratory Endpoints

PK profile of carbidopa (Cohort 4 only) for 120 minutes following dosing with INP103 and where possible, determine AUC_{0-2h} , C_{max} and T_{max} .

3.3. Statistical Hypotheses

There are no formal statistical hypotheses defined for this Phase IIa study. All data will be compared descriptively.

3.4. Pharmacokinetic and Pharmacodynamic Hypotheses

There are no formal statistical hypotheses for PK and PD_{yn} for this Phase IIa study.

4. STUDY DESIGN

This is a Phase IIa randomized, double-blind, placebo controlled, single dose study to compare the safety, tolerability and PK/PD of nasal L-dopa in the presence of decarboxylase inhibitor (DCI) during an OFF episode.

Subjects will attend a Screening visit up to Day -21 (Visit 1). During the maximum 21-day window between Screening and study dosing (i.e. between Visit 1 and Visit 3), subjects deemed eligible from Visit 1 assessments will be invited to attend a second Screening visit (Visit 2) to the clinical unit to confirm dopamine responsiveness. For Visit 2, subjects will discontinue all PD medication from 22:00 the previous evening (i.e. Day -10 if attending Visit 2 on Day -9). At the discretion of sites, patients may be domiciled overnight for this visit. In addition, subjects will miss their usual morning L-dopa dose (50–250 mg). Missed morning dose will include missed DCI if a DCI (such as benserazide if Madopar, or carbidopa if Sinemet) comprises the subject's usual PD medication. At the start of Visit 2, the subject will have their OFF state confirmed using the full Movement Disorder Society Unified Parkinson's Disease Rating Scale (MDS-UPDRS) scale. The subject will then take their usual L-dopa containing medication (including DCI if part of the subject's usual PD medication) and repeat the MDS-UPDRS Part III test (motor examination) at 15, 30, 45, 60, 90 and 120 minutes thereafter for C1, C2, C3, and at 30, 60, 90 and 120 minutes for C4. Subjects showing at least a 30% improvement in MDS-UPDRS Part III score during this visit will be deemed to be dopamine responsive and will be eligible to be randomized and return for Visit 3 on Day 0.

If subjects usually obtain a satisfactory response to their OFF treatment (in their opinion), but fail to do so on Visit 2, the Investigator, with sponsor approval, is allowed to repeat the Visit 2 response assessment within the screening period to determine if a more representative response (i.e. >30% improvement in MDS-UPDRS score) can be obtained.

Subjects may be domiciled at the clinic overnight to enable scheduled assessments on the morning of, and prior to, Visit 2 (standard medications) and Visit 3 (test article) dosing, or will have transport provided to ensure they arrive at the clinical research unit on the morning of Visit 2 and Visit 3. Regardless of time of arrival at the study site, all subjects will be required to suspend dosing of usual PD medication (e.g. regular Madopar® or Sinemet® doses, DAS and/or COMT inhibitors doses and any required anti-OFF medication [e.g. Madopar rapid]) from 22:00 pm on Day-1, the day prior to study dosing. Suspension of usual PD medication will include on the morning of Day-0.

On Day-0, upon arrival at the research site (or upon waking if the subject was domiciled overnight at the research unit), and at 60 ± 5 minutes before dosing with INP103 or placebo, all subjects in Cohorts 1, 2, and 3 will take oral benserazide hydrochloride (benserazide) 25 mg (provided by the Sponsor). Subjects in Cohort 4 will NOT receive oral benserazide. Subjects who arrive at the study site on Day-0 (or who were domiciled overnight) and are determined by the Investigator to be in an ON state up to the scheduled time of dosing will not be dosed and will be excluded from further study participation but may be replaced at Sponsor's discretion.

On their scheduled day of dosing (Day-0; or on arrival at the unit on Day-1), eight subjects in each of three dose cohorts (35, 70 or 140 mg of INP103 L-dopa) and at least eight (8) (maximum 12) subjects in Cohort 4 (70/7.0 mg of INP103 L-dopa:carbidopa) will be randomized in a 3:1 fashion to one of two treatment arms. All subjects in Cohorts 1, 2 and 3 will receive oral benserazide 25 mg 60 ± 5 minutes before dosing with the study drug. Subjects in Cohort 4 will not receive oral benserazide before dosing with the study drug:

- INP103 (n=6 or maximum 9 in Cohort 4)

CONFIDENTIAL AND PROPRIETARY

- Placebo (n=2 or maximum 3 in Cohort 4)

Use of usual anti-PD medication (usual regular dosing [e.g. regular Madopar or Sinemet] and use of anti-OFF treatment, if required) may resume at 120 minutes after use of INP103 or placebo.

Subjects will be monitored for 7 days after the final administration of INP103 or placebo. All subjects will be observed as in-patients for at least 240 minutes post-dosing at visit 3. Follow-up evaluations will occur 7 days after dosing.

Once dosing has been completed (for all subjects) in a cohort, data will be collected through to 7 days post dosing (Visit 4, follow-up). This data will then be reviewed by a Safety Monitoring Committee (SMC) for cohorts 1 and 2 only, and if no INP103 or placebo-related serious adverse events (SAEs) or severe AEs have been reported, dosing may commence in the next cohort. The SMC will have 7-14 days between dosing of cohorts to review safety (and available PK data) compiled by the site and the biostatistics analysis provider.

Interim analysis of data will be conducted upon completion of Cohort 1 and 2 study procedures, at the discretion of the Sponsor, depending on rate of recruitment. In this scenario, Cohort 1 and 2 data will be soft-locked, patients may be unblinded and tables, listings, and figures of collected data will be produced. Unblinding of Cohort 1 and 2 data will not jeopardize blinding of any enrolled Cohort 3 or 4 subjects at the time of the interim analysis.

4.1. Sample Size Considerations

4.1.1. Sample Size Justifications

Thirty-two (32) subjects (8 per dose group) are considered sufficient for assessment of safety and tolerability of SADs of INP103. Cohort 4 may enroll an additional 4 patients (for a maximum of 12) under the same randomization scheme (3:1). With at least eight subjects per group, the study has 80% power to detect an improvement of 13 points from baseline compared to placebo in MDS-UPDRS Part III scores within each dose level, assuming a standard deviation of 11 points, using a two-sided significance level of 0.05. This study is not powered for between-group comparisons of the PDyn endpoints.

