12.1. Sample Size Calculation

Thirty-two (32) subjects (8 per dose group) are considered sufficient for assessment of safety and tolerability of SADs of INP103. However, we are proposing that Cohort 4 may enrol an additional 4 patients (for a maximum of 12) under the same randomization scheme (3:1). With at least eight subjects per group, the study has 80% power to detect an improvement of 13 points from baseline in MDS-UPDRS Part III scores within each dose level, assuming a standard deviation of 11 points, using a two-sided significance level of 0.05. This study is not powered for between-group comparisons of the pharmacodynamic endpoints.

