At least thirty-two (32) subjects are considered sufficient for assessment of safety and tolerability of SADs of INP103. Furthermore, with 8 subjects per cohort, the study has 80% power to detect a difference in improvement of 13 points compared to placebo from pre-dose in MDS-UPDRS Part III scores within each dose level, assuming a standard deviation of 11 points.

Analysis Populations:

If there is no difference between 2 (or more) populations, the analyses will not be repeated but will be assigned to the following populations – which are listed here in order:

Intention-to-Treat (ITT) Population: All subjects who randomized into this study, regardless of receiving the study drug (INP103 or placebo) or not, will be included in this population. In general, all data listings and subject disposition, will be generated on this population except PK and PDyn results. Summaries of demographics, prior and concomitant medications will be produced using this population.

Benserazide Safety Population: All subjects who receive any amount of benserazide (as provided by the Sponsor) will be included in the Benserazide Safety Population. This population will be used for the analysis of the safety data collected after receiving benserazide (as provided by the Sponsor) and before receiving INP103 or placebo. This population will not be applicable to Cohort 4.

Safety Population: All subjects who receive any amount of INP103 or placebo will be included in the Safety Population. The data will be analyzed according to the treatment received. All safety results will be generated on Safety Population.

PK Population (PKP): All subjects who receive placebo or the full planned dose of INP103 or active treatment subjects who receive partial dose (as reported by clinical observation of the number of puffs delivered) with exposure reasonably consistent with subjects who received the same actual dose amount (to be determined by clinical observation and review of data by pharmacokineticist) and have sufficient samples collected for calculation of at least one PK parameter through non-compartmental analysis will be included in the PK Parameter Population (PKP). The PK parameter data will be analyzed according to the treatment received. PK parameter results will be produced using this population. Placebo subjects included in the PKP will only have PK parameters derived from uncorrected L-dopa concentrations.

Safety and Tolerability:

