4.2. Randomization

At least thirty-two (32), maximum 36, subjects will be randomized, and as this is a multi-center study, centralized randomization will be performed. Treatment assignment will be randomized by blocks of 4 in sequential cohorts, with subjects assigned to either INP103 with or without carbidopa, or placebo delivered via the POD device with one, two, or four actuations, depending on cohort. Ratio of active to placebo assignment is 3:1. Randomization may occur on the day prior to (Day-1) or day of (Day-0) Visit 3 dosing. Subjects who are randomized but not dosed may be replaced at the Sponsor's discretion.

| Cohort | Treatment (Study Drug) |
|--------|--|
| 1 | INP103 35 mg L-dopa (n=6); Placebo (n=2) |
| 2 | INP103 70 mg L-dopa (n=6); Placebo (n=2) |

CONFIDENTIAL AND PROPRIETARY

| | |
|---|---|
| 3 | INP103 140 mg L-dopa (n=6); Placebo (n=2) |
| 4 | INP103 70 mg L-dopa/7.0 mg carbidopa (n=6, maximum 9); Placebo (n=2, maximum 3) |

For more detail, please refer to final Randomization Plan and Specification (version 3.0, dated: 22 FEB 2019).

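### The stated 80% power for 13 points compared to placebo at each dose does not follow from the planned arms: with SD 11 for the change it is about 52–56% (65–68% for Cohort 4 at its maximum)

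*SAP*

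**What the plan says.** The 80% figure appears in four places, attached to two different quantities.

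- **SAP 4.1.1:** "With at least eight subjects per group, the study has 80% power to detect an improvement of 13 points from baseline compared to placebo", within each dose level, SD 11, two-sided 0.05. The next sentence reads "This study is not powered for between-group comparisons of the PDyn endpoints".
- **SAP synopsis (Statistical methods):** "with 8 subjects per cohort, the study has 80% power to detect a difference in improvement of 13 points compared to placebo", within each dose level, SD 11. The protocol synopsis has the same sentence. Neither synopsis says that the study is not powered for between-group comparisons.
- **Protocol 12.1:** "With at least eight subjects per group, the study has 80% power to detect an improvement of 13 points from baseline in MDS-UPDRS" Part III, with the same SD and significance level and no mention of placebo. It then adds "This study is not powered for between-group comparisons of the pharmacodynamic endpoints".

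On arm sizes, SAP 4.2 gives six INP103 and two placebo subjects in each of Cohorts 1 to 3. Cohort 4 has six and two, rising to at most nine and three. SAP 7.1 pools placebo over all cohorts. SAP 10.2 estimates each treatment group against placebo from the MMRM, with 95% confidence intervals, and says that the focus is on change within each group.

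**The concern.** *Compared to placebo* and *difference in improvement* describe a between-group contrast. The eight per group or cohort in those sentences is not the size of any dose arm; it is six active plus two placebo. No dose has eight INP103 subjects at the planned minimum.

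INP103 versus placebo on motor function is a secondary objective (SAP 3.1.2), and every dose–placebo difference will be reported with an interval. A reader who relies on a synopsis is told that this comparison has 80% power at each dose. That reader could take a wide, inconclusive interval as evidence against a 13-point effect. On the stated assumptions, the design would miss such an effect nearly half the time at most doses.

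**Working it through.** **Inputs.** Difference 13, SD 11 and two-sided 0.05 come from SAP 4.1.1. Arm sizes come from SAP 4.2. Pooled placebo (SAP 7.1) is 2+2+2+2 = 8, or 2+2+2+3 = 9 if Cohort 4 is expanded.

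**Assumption.** SD 11 is the SD of the change score at a single time point. The documents do not say what it is the SD of, and SAP 4.1.1 names no time point.

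**Formulas.** Power is the probability that a noncentral t exceeds the 0.975 t quantile.
- Within group: SE = 11/√n
- Dose v placebo: SE = 11·√(1/n₁ + 1/n₂)
- Noncentrality = 13/SE

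Each range runs from a test using only the subjects in that comparison to one with error variance pooled over the five treatment groups. The pooled error df are 32−5 = 27, or 26 with the baseline covariate; at 36 subjects they are 31 or 30. The pooled version approximates the planned MMRM at 30 minutes, when all four cohorts are assessed.

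**1. The plan's figure as a within-group change (Protocol 12.1).**

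| n | SE | Noncentrality | One-sample t | Error pooled over five groups |
|---|---|---|---|---|
| 8 (as stated) | 3.89 | 3.34 | 81.7% | – |
| 6 (planned per dose) | 4.49 | 2.89 | 64.2% | 79.6–79.7% |
| 9 (Cohort 4 maximum) | 3.67 | 3.55 | 87% | about 93% |

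So 80% is approximately reproduced within group, either by a one-sample t with n=8, which no dose arm has at the planned minimum, or at n=6 with pooled error.

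**2. The plan's figure as a difference from placebo (SAP 4.1.1 and both synopses).**

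| Arms | SE | Noncentrality | Power for 13 points | Difference for 80% power |
|---|---|---|---|---|
| 8 v 8 (eight per group read literally) | 5.50 | 2.36 | 59.5% (two-sample t) | 16.6 |
| 6 v 8 (32 subjects) | 5.94 | 2.19 | 52.1–56.0% | 17.3–18.1 |
| 6 v 9 (other doses, Cohort 4 expanded) | 5.80 | 2.24 | 54.6–58.4% | 16.8–17.6 |
| 9 v 9 (Cohort 4 expanded) | 5.19 | 2.51 | 65.3–68.0% | 15.0–15.5 |

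Worked example for 6 v 8: 1/6 + 1/8 = 0.2917, its square root is 0.540, 11 × 0.540 = 5.94, and 13/5.94 = 2.19. The critical value is 2.18 on 12 df and about 2.05 on 27 df.

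**3. Sensitivity to the SD, at 6 v 8.**

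| SD | 8 | 9 | 10 | 11 | 12 | 13 |
|---|---|---|---|---|---|---|
| Power | 79–83% | 69–73% | 60–64% | 52–56% | 45–49% | 40–43% |

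Reaching 80% at 6 v 8 needs an SD of about 7.9–8.3.

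**The case against.** The strongest reply is that the documents already deal with this. SAP 4.1.1 and Protocol 12.1 both disclaim between-group power. Protocol 12.1 states the 80% as a change from baseline. SAP 3.3 sets no formal hypotheses, SAP 10 treats the motor analyses as exploratory, and both synopses put the focus on within-group estimation. All of that stands, and it limits the consequence. It does not correct the sentence. In SAP 4.1.1 the disclaimer contradicts the claim just before it, and the synopses have no disclaimer. Under Protocol 12 the SAP supersedes where the two differ, so the governing text is the one that mentions placebo.

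The second reply is that the percentages depend on an undefined SD. That is correct. The planned models adjust for baseline, and if 11 is the SD of the raw score, the residual SD could be smaller. A residual SD near 8 would bring 6 v 8 to about 80%. The documents give no baseline correlation to support such a value, so every figure here is conditional.

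The third reply is that deleting *compared to placebo* would be enough. It would remove the contradiction, but it would leave a within-group 80% tied to eight subjects when each dose has six. By one-sample t that power is 64.2%.

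A reader might also infer that the trial is too small. The documents do not support that: "Thirty-two (32) subjects (8 per dose group) are considered sufficient for assessment of safety and tolerability of SADs of INP103", so the sample size does not rest on motor power. Nor can one infer how the 80% was obtained. More than one calculation lands near it, and the documents do not state the basis.

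**Conclusion.** The power statement in SAP 4.1.1 and both synopses is wrong as written and should be corrected. With SD 11 for the change at a single time point and two-sided 0.05, no single dose has 80% power against pooled placebo for 13 points. The overstatement is 24–28 percentage points at 6 v 8 (80 minus 56 or 52). If Cohort 4 is expanded, it is 22–25 points for the other doses and 12–15 for Cohort 4. A smaller baseline-adjusted residual SD would narrow the gap. Averaging over time points would also change the variance, in a way the documents do not allow to be calculated.

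The within-group reading is defensible at n=6 only with error pooled over the five groups. Enrolment, analyses and decisions are unaffected.

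**What to change.** In SAP 4.1.1 and the SAP synopsis:

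1. Delete *compared to placebo*, and in the synopsis also *a difference in improvement*.
2. State what SD 11 is the SD of.
3. Restate the power for a 13-point within-group change at the real arm sizes, naming the method. At n=6 it is 64% by one-sample t, or about 80% with error pooled over five groups. At n=9 in an expanded Cohort 4 it is 87% or about 93%.
4. Add:

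> Against pooled placebo, assuming SD 11 for the change at a single time point, power for a 13-point difference at a single dose is about 52–56% with 32 subjects (6 v 8; 80% power needs about 17–18 points). If Cohort 4 is expanded to 12, it is about 55–58% for the other doses (6 v 9; about 17–17.5 points) and 65–68% for Cohort 4 (9 v 9; about 15–15.5 points).

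5. Keep the sentence in 4.1.1 that disclaims between-group power, and repeat it in the SAP synopsis.

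The safety justification for 32 subjects needs no change. Align the protocol synopsis and Protocol 12.1 at the next protocol amendment.

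**Cost.** A few sentences in two places of the SAP, which SAP 2 allows to be amended before final database lock. The sponsor must also look up the basis of the SD and of the 80%. A separate protocol amendment, which would go to the ethics committee under Protocol 17.1, is not needed for this alone.
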